**c. Informed Consent Process:**

1. In obtaining and documenting informed consent, investigators and the research team will comply with the applicable regulatory requirements, Good Clinical Practice, and ethical principles. The written Informed Consent (IC) Form will be approved by the Institutional Review Board/Ethics Committee (IRB/EC) prior to starting the study.
2. Potential subjects will be informed about the scope of the study, expected benefits, and possible risks. They will also be informed that participation is voluntary and can be terminated at any time without reason.
3. The extent of confidentiality of subject records is defined in the IC and applicable data protection legislation will be provided to the parent/legal guardian. Subjects will be informed that the sponsor or sponsor's designee, monitor, auditor, IRB/EC, and the regulatory authority (ies) will be granted direct access to the subject's original medical records for verification of clinical trial procedures and/or data, without violating laws and regulations. By signing a written IC form, the subject's legally acceptable representative is authorizing such access.
4. The IC will be explained thoroughly to the subject. Ample time will be given to answer all questions. A signature will be obtained prior to any study procedures. A signed and dated copy of the IC will be given to the subject's parents/guardians and subject.
5. Subjects may also receive IRB approved information about the vaccines to be used in the study.
6. Assents will be used for children in this study (verbal assents for children 3-6 years, if applicable, and signed assents for children 7-17 years of age).

**d. Exclusion of Women, Minorities, and Children (Special Populations):**

**Comparison of High vs. Standard Dose Flu Vaccine in Pediatric Stem Cell Transplant Recipients**

**DMID Protocol Number 16-0117**

**Protocol Version 8.0**

**Date: 9/12/2019**

This study will be inclusive of children 3-17 years of age HSCT recipients who meet the inclusion/exclusion criteria, regardless of religion, sex, or ethnic background.

**e. Subject Confidentiality:**

1. All information will be in the research record that will be handled by the research personnel. The results of the research study may be published, but volunteers' names or identities will not be revealed. Records will remain confidential.
2. In order to maintain subject confidentiality, records will be kept locked and results of tests will be coded to prevent association with volunteers' names. This confidentiality is extended to cover testing of biological samples in addition to the clinical information relating to participating subjects. Volunteers' records will be available to the FDA, NIH, external monitors, and the IRB.
3. The study protocol, documentation, data and all other information generated will be held in strict confidence. No information concerning the study or the data will be released to any unauthorized third party, without prior written approval of the sponsor.
4. The following confidential information will be collected into folders and stored in a safe, locked location, identified only by code number: age, gender, race, family history, social history, full address, phone number (home, cell, and work), and date of birth, fax number, secondary name, birth history, and contact number, and email address of the subject's parent/legal guardian.
5. The records will be sent to storage after study completion and data analysis.
6. Serum samples will be collected during this study and stored with their subject ID as the only identifiers. Laboratory assays containing data from the study will be labeled only with volunteer code numbers.
7. The information in the REDCap or ON-Core database will only include non-identifiable information.

**f. Study Discontinuation:**

If the study is discontinued, enrolled subjects will continue to be followed for safety assessments. No further doses of vaccine will be administered. Samples will be stored at Vanderbilt.

**g. Future Use of Stored Specimens:**

Subjects will be asked for permission to keep any remaining specimen for possible use in future research studies, such as testing for antibodies against other viruses or bacteria. By the end of the study, all samples will be stored at Vanderbilt. The samples may be shared with other investigators. The samples will not be sold or used directly for production of any commercial product. No human genetic tests will be performed on samples prior to obtaining new, written permission (consent) from the subject. Each sample will be labeled with a unique number to protect the subject's confidentiality. There is a small risk of loss of confidentiality. The samples will be stored indefinitely.

There are no benefits to subjects in the collection, storage, and subsequent research use of specimens. Reports about future research done with subject's samples will NOT be kept in their health records, but subject's samples may be kept with the study records or in other secure areas. Subjects can decide if they want their samples to be used for future research or have their samples destroyed at the end of the study. A subject's decision can be changed at any time prior to the end of the study by notifying the study doctors or nurses in writing. However, if a subject consents to future use and some of their blood has already been used for research purposes, the information from that research may still be used.

**19. Data Handling and Record Keeping:**

The investigator is responsible to ensure the accuracy, completeness, legibility, and timeliness of the data reported. All data collection forms should be completed in a neat, legible manner to ensure accurate interpretation of data. Black or blue ink is required to ensure clarity of reproduced copies. When making a

change or correction, cross out the original entry with a single line and initial and date the change. Do not erase, overwrite, or use correction fluid or tape on the original.

**a. Data Capture Methods:**

For all the sites, the data will be entered into a standardized, secured database: **REDCap** (Research Electronic Data Capture) system. REDCap is a secure, web-based application designed to support data capture for research studies, providing: 1) an intuitive interface for validated data entry; 2) audit trails for tracking data manipulation and export procedures; 3) automated export procedures for seamless data downloads to common statistical packages; and 4) procedures for importing data from external sources. The research team at each site will be given a user name and pass codes to be able to enter data from their sites locally.

At Vanderbilt, safety data from REDCap maybe transferred to **On-line Clinical Oncology Research Environment = ONCORE (OnCore)** is a highly secure, web based, cancer specific, and customizable system that provides fully integrative clinical data management and study administration capabilities developed in an ongoing collaborative effort with National Cancer Institute (NCI) designated Comprehensive Cancer Centers. It fully integrates study administration functionality including protocol tracking, patient registration, NCI reporting, review committee tracking, and SAE tracking, with clinical data management functionality including electronic case report forms (eCRF) design, clinical data capture, protocol and regulatory compliance monitoring. Also the system is capable in storing basic protocol information (e.g., IRB approval dates, dates for annual renewals, etc.) and clinical trials research data. Oncore allows the investigator to define specific protocol requirements and generate data collection forms. Creation of the data collection form is done with a single button click after the parameters of an individual protocol have been specified. Oncore permits specification of study protocols, management of patient enrollment, clinical data entry and viewing, and the generation of patient or study-specific reports based on time stamping. OnCore is embedded with a comprehensive domain repository of standard reference codes and forms to promote standardization. The sources for the repository include CDUS, CTC, CDEs from NCI, ICD, MedDRA and various best practices from contributing NCI-designated Comprehensive Cancer Centers. OnCore provides several reporting features specifically addressing NCI Summary 3 and Summary 4 and other reporting requirements. Data may also be exported in a format suitable for import into other database, spreadsheets or analysis systems (such as SPSS). This system will be used to manage all Vanderbilt Ingram Cancer Center (VICC) clinical trials data. OnCore is maintained and supported in the VICC Clinical and Research Informatics Resource. A copy of the paper records will be retained for at least 7 years after completion of the study. The information stored in the ONCORE and REDCap database will be kept indefinitely.

---

**20. Publication Policy:**

The intention of this study is to publish the data from this trial. The International Committee of Medical Journal Editors (ICMJE) member journals have adopted a trials-registration policy as a condition for publication. This policy requires that all clinical trials be registered in a public trials registry such as ClinicalTrials.gov, which is sponsored by the National Library of Medicine. Other biomedical journals are considering adopting similar policies.

**21. Certificate of Confidentiality:**

To protect privacy, we have received a Certificate of Confidentiality. With this Certificate, the researchers cannot be forced to release information that may identify the research subject, even by a court subpoena, in any federal, state, or local civil, criminal, administrative, legislative, or other proceedings. The researchers will use the Certificate to resist any demands for information that would identify the subject, except as explained below.

**Comparison of High vs. Standard Dose Flu Vaccine in Pediatric Stem Cell Transplant Recipients**

**DMID Protocol Number 16-0117**

**Protocol Version 8.0**

**Date: 9/12/2019**

The Certificate cannot be used to resist a demand for information from personnel of the United States Government that is used for auditing or evaluation of federally funded projects, like this study, or for information that must be released in order to meet the requirements of the Federal Food and Drug Administration (FDA).

A Certificate of Confidentiality does not prevent the subject from voluntarily releasing information about themselves or their involvement in this research. If any person or agency obtains a written consent to receive research information, then the researchers may not use the Certificate to withhold that information.

The Certificate of Confidentiality does not prevent the researchers from reporting without the subject's consent, information that would identify the subject as a participant in the research project regarding matters that must be legally reported including: child and elder abuse, sexual abuse, or wanting to harm themselves or others.

The Certificate of Confidentiality applies *only* under US law.

1. INTRODUCTION

1.1 Overview

This phase II immunogenicity and safety trial compares a high-dose trivalent inactivated influenza vaccine (HD-TIV) to standard-dose quadrivalent inactivated influenza vaccine (SD-QIV) in pediatric hematopoietic stem cell transplant (HSCT) recipients. Participants were randomized to receive either two doses of 0.5 mL HD-TIV (60 μ g of each influenza antigen) or two doses of 0.5 mL SD-QIV (15 μ g of each influenza antigen) of the season-specific vaccine 28-42 days apart. This statistical analysis plan (SAP) describes the methods for the final analysis.

1.1.1 *Study sites*

Study subjects were recruited from the Outpatient Pediatric Oncology/HSCT Clinics or Clinical Trial Centers at the sites listed in Table 1.

1.1.2 *Schedule of assessments*

Study subjects were evaluated according to the following general schedule of assessments.

- a. Screening: Subjects were screened by history and physical exam to ensure all eligibility criteria were met.
- b. Study Visit 1: First blood sample collected; first vaccine administered.
- c. Study Visit 2 (28-42 days following Study Visit 1): Second blood sample collected; second vaccine administered; visit window was 28-42 days following Visit 1.
- d. Study Visit 3 (28-42 days following Study Visit 2): Third blood sample collected. Visit window was 28-42 days after administration of the second vaccine dose.
- e. Study Visit 4 (180 \pm 42 days following Study Visit 2): Fourth blood sample collected. For the 2016/2017 enrollment season, visit window was 180 \pm 28 days following Visit 3. For the 2019/2020 enrollment season, this visit was optional.

1.1.3 *Repeaters*

A subset of subjects enrolled and vaccinated in 2016-17, 2017-18, or 2018-19 were re-enrolled for a maximum of one subsequent year. For example, subjects enrolled in 2016-17 could re-enroll in 2017-18 as repeaters. Subjects could only enroll as a repeater one time, the year following their original enrollment, and must have received at least one vaccine to be eligible as a repeater. Subjects enrolled as repeaters received two doses (separated by 28-42 days) of the same vaccine formulation (HD-TIV or SD-QIV) that they were randomized to receive in their first year of enrollment, again with investigators blinded to vaccine formulation.

1.1.4 *Randomization*

Randomization to HD-TIV or SD-QIV was frequency-matched within each site to ensure balance between the groups and was implemented using the Randomization Module within Vanderbilt's REDCap database. For subjects \geq 12 months post-transplant, randomization was stratified on

treatment for graft versus host disease (GVHD) with systemic steroids. For subjects < 12 months post-transplant, randomization was stratified on meeting any of the following: (a) treatment for GVHD with systemic steroids, (b) history of alemtuzumab, (c) history of anti-thymocyte globulin, (d) receipt of a cord graft, (e) haploidentical transplant, or (f) post-transplant cyclophosphamide. Repeaters retained randomization from initial enrollment and were *not* re-randomized.

1.2 Study objectives

Immunogenicity and safety objectives are organized into subsections below. To avoid repetitive language, *all* objectives apply to the target study population (namely, pediatric HSCT recipients).

1.2.1 *Objectives for HAI immunogenicity outcomes*

The primary objective is to determine whether two doses of HD-TIV is associated with a higher geometric mean HAI titer to either influenza A antigen (H1N1 and H3N2, evaluated separately) compared to two doses of SD-QIV.

The secondary objectives pertaining to HAI immunogenicity outcomes are as follows:

- To determine whether two doses of HD-TIV is associated with a higher geometric mean HAI titer to influenza B antigens as compared to two doses of SD-QIV.
- To determine whether two doses of HD-TIV is associated with higher odds of seroconversion or seroprotection in *any* HAI antigen as compared to two doses of SD-QIV.
- To compare HAI immunogenicity for each antigen between the following groups: (a) one dose of HD-TIV vs. one dose of SD-QIV, (b) one dose of HD-TIV vs. two doses of HD-TIV, and (c) one dose of SD-QIV vs. two doses of SD-QIV.

The tertiary objectives pertaining to HAI immunogenicity outcomes are as follows:

- To compare HAI immunogenicity for each antigen between the one dose of HD-TIV and two doses of SD-QIV.
- To determine whether time post-transplant, subject age, or GVHD status (presence/absence) modifies the association between vaccination group and HAI response.
- To characterize the relationship between HAI titers, ex-vivo T and B cell phenotype, and ex-vivo influenza-specific T and B cell response in subjects receiving either HD-TIV or SD-QIV.
- To compare HAI immunogenicity outcomes between treatment groups (one dose or two doses of HD-TIV vs. one dose or two doses of SD-QIV, respectively) among those enrolled for a second year (repeaters).

1.2.2 *Objectives for safety outcomes*

The primary objectives for safety outcomes are to compare the frequency/severity of solicited local injection site adverse events (AEs) and systemic AEs between HD-TIV and SD-QIV following the first dose and following the second dose. The secondary objective is to compare safety outcomes between treatment groups among those enrolled for a second consecutive year (repeaters).

1.2.3 *Further exploratory objectives*

- To compare the persistence of HAI and microneutralization (MN) titers between HD-TIV and SD-QIV across all four antigens seven months after the final vaccine dose.
- To compare MN and NAI responses between subjects receiving HD-TIV and SD-QIV in the first year.
- To compare MN and NAI titers between treatment groups (two doses of HD-TIV vs. two doses of SD-QIV) among those enrolled for a second year, and compare them to HAI responses.
- To compare influenza virus detection during influenza season between treatment groups (two doses of HD-TIV vs. two doses of SD-QIV).
- To evaluate the correlation between HAI and baseline MN responses.

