## 2. Prior Influenza Vaccine Trials in HSCT Recipients:

Influenza vaccination is the primary mode for prevention of influenza infection. Protection is primarily mediated by virus-specific antibodies that depend on an intact humoral response. Both B cell and T cells responses are impaired in HSCT recipients, functional recovery of B and T lymphocytes can take up to 2 years or even longer. Limited data are available regarding influenza vaccine responses in pediatric HSCT recipients because the majority of influenza vaccine trials have been conducted in adult HSCT recipients. Only 5 of these trials included children, and only one exclusively included children, with total enrollment of 5 subjects. Therefore, dedicated influenza vaccine trials in pediatric HSCT patients are needed.

Despite limited clinical data for influenza vaccine efficacy in this population, yearly vaccination is recommended, beginning 3-6 months after HSCT. However, the optimal post-transplantation vaccine schedule has not been established. Existing data for influenza vaccination in HSCT recipients are primarily from subjects who received influenza vaccination between 6 months and 3 years after HSCT. Thus, little data exist to support vaccinating pediatric HSCT recipients earlier than 6 months or later than 3 years post-transplant. The percentage of HSCT recipients that achieve seroprotective hemagglutinin inhibition (HAI) titers (defined as  $\geq 1:40$ ) one month after standard influenza vaccination is very low when compared to healthy controls. While this impaired vaccine-induced immune response is likely due to incomplete immune reconstitution or immunosuppressive therapies, the exact immune mechanisms of HSCT recipients' poor response to influenza vaccination are not well described. Notably, graft versus host disease (GVHD), low number of CD19+ B cells, and earlier timing of vaccination post-transplant have been implicated as factors associated with lower titers after influenza vaccine.

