The authors in the 2013 publication, *European Guidelines for the Prevention and Management of Influenza in HSCT Patients*, recommends yearly inactivated influenza vaccine (IIV) each influenza season to HSCT recipients; vaccine is preferably given prior to the influenza season, usually at least 3 months after HSCT and a second dose of vaccine after 3-4 weeks is advised, although the second dose may only have marginal benefit. Results from trials comparing two doses of influenza vaccine are conflicting: some suggest no benefit with 2 doses, while others demonstrate an increase in influenza titers after the second dose in HSCT recipients. The trials that used ASO3-adjuvanted H1N1 vaccine, which is not available in the United States, suggest higher titers are induced with a 2-dose schedule.

In contrast, the 2013 *IDSA Clinical Practice Guidelines for Vaccination of the Immunocompromised Host* recommends yearly vaccine with IIV and it can be administered 6 months after HSCT or as early as 4 months after HSCT during an influenza outbreak. Thus, both the optimal timing of influenza vaccination and the ideal number of doses needed remain unclear. A better understanding of immune responses to influenza vaccination (e.g. B and T cell responses to influenza antigens) is also necessary. A promising strategy and

only immediate practical alternative to overcome the poor immunogenicity of influenza vaccine may be to increase the antigen dose in the vaccine. This strategy has been successful in individuals  $\geq 65$  years, a group with a historically poor response to influenza vaccines compared to healthy young adults.

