## Proven clinical influenza illness is any breakthrough influenza illness confirmed by laboratory testing (i.e. Rapid antigen assay, PCR, virus culture, ,etc.

^^ Optional for repeaters in the 2019-20 season

**5. Treatment Groups:** There will be two groups – HD-TIV versus standard dose QIV. The children will be randomized in a 1:1 HD-TIV (100 subjects) versus standard dose QIV (100 subjects) for current enrollment season.

Treatment Group	Target # (all study years)
Group 1 0.5 mL HD-TIV	100
Group 2 0.5 mL standard dose QIV	100

**a. Randomization:** Subjects will be randomized 1:1 to either HD-TIV or standard dose QIV. Randomization will be frequency-matched within each site to ensure balance between the groups and will be implemented using the Randomization Module within Vanderbilt's REDCap database. The investigational pharmacy at each of the 9 institutions will distribute the assigned study vaccine. Because we are evaluating the immunogenicity of early timing of influenza vaccine post-transplant, we will limit enrollment to 60 (30%) subjects to  $\geq 12$  months post-transplant.

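### The one-versus-two-dose contrasts (SAP 1.2.1, Table 3 rows 3-5) are before/after differences: dose 2 and elapsed time share one coefficient, and the SAP does not say so

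*SAP*

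**What the plan says.** Allocation is by formulation only. Protocol C.5a states "Subjects will be randomized 1:1 to either HD-TIV or standard dose QIV", and SAP 1.1 states "Participants were randomized to receive either two doses of 0.5 mL HD-TIV", with the same two-dose schedule for SD-QIV. Neither document has a one-dose arm or a delayed-second-dose arm.

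SAP 1.1.2 describes Visit 2 (28-42 days after Visit 1) with the words "Second blood sample collected; second vaccine administered". For Visit 3 it says "Visit window was 28-42 days after administration of the second vaccine dose". One dose is therefore the Visit 2 sample, and two doses is the Visit 3 sample from the same children.

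SAP 1.2.1 presents the following as comparisons between groups: "b) one dose of HD-TIV vs. two doses of HD-TIV, and (c) one dose of SD-QIV vs. two doses of SD-QIV". A tertiary objective is "To compare HAI immunogenicity for each antigen between the one dose of HD-TIV and two doses of SD-QIV". Table 3 tests these through exp(beta2), exp(beta2+beta3) and exp(beta2-beta1). In the SAP 5.1 model beta2 is the coefficient on the Visit 3 indicator, and the adjustment covariates are pre-treatment only. SAP 5.2 and 5.3 carry the same structure over to seroprotection and seroconversion. Protocol 17b likewise crosses formulation with dose number.

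Neither document states an assumption of no time effect for these contrasts, or a limitation.

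**The concern.** The protocol treats dose number as unsettled: in B.2 it says that "the ideal number of doses needed remain unclear". A reader of a results table with rows labelled by dose number and tested against a null will take a significant row 3 or 4 as support for the second dose, and a flat one as evidence against it.

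The documents themselves describe things other than dose 2 that can change between the visits:

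- Immune recovery: in B.2, "functional recovery of B and T lymphocytes can take up to 2 years or even longer", in children enrolled 3-35 months after transplant.
- Infection: enrollment continues during influenza season (protocol C.1).
- Immunoglobulin: IVIG/SCIG may be given on the day of dose 2 (protocol 14, Visit 2), and the protocol takes an extra serum sample when it is.

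A continuing rise or waning from dose 1 adds to these. The direction of the net effect is unknown.

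**Working it through.** **Inputs.** From the documents: arms, doses and visit windows (SAP 1.1; protocol C.5a); the model (SAP 5.1); two-sided alpha 0.05 (SAP 2.5); 80 evaluable children per arm (protocol 17a). Assumed, because the documents give no value: the SD of the within-child change from Visit 2 to Visit 3, and the ratio by which titres would have changed without dose 2 (the time ratio).

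**1. The plan's own figure.** For 40% versus 20% with 80% power, the unpooled formula gives (1.96+0.842)^2 x (0.40x0.60 + 0.20x0.80) / 0.20^2 = 7.85 x 0.40 / 0.04 = 78.5, so 79 per arm. The pooled formula gives 82. The plan's 80 is reproduced within rounding, and 80/(1-0.20) = 100 per arm, 200 in total. This sizing concerns formulation. No figure is given for one versus two doses.

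**2. What the rows estimate.** The model's log-scale means, covariates aside, are:

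| | Visit 2 | Visit 3 |
|---|---|---|
| SD-QIV | b0 | b0+b2 |
| HD-TIV | b0+b1 | b0+b1+b2+b3 |

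- Row 3 = SD Visit 3 minus SD Visit 2 = b2.
- Row 4 = HD Visit 3 minus HD Visit 2 = b2+b3.
- Row 5 = SD Visit 3 minus HD Visit 2 = b2-b1.
- HD minus SD at Visit 3 = b1+b3, whereas Table 3 row 1 assigns b3 to that comparison.

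**3. Can dose 2 be separated from time?** Let dSD and dHD be the log effects of dose 2 at Visit 3 relative to staying at one dose, and w the log change that would have occurred anyway. Then b2 = dSD + w, and b2+b3 = dHD + w if w is common to both arms.

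- Within an arm there are 2 means and 3 unknowns (Visit 2 level, d, w): rank 2 of 3.
- With both arms and a common w there are 4 means and 5 unknowns: rank 4 of 5.
- Not estimable: dSD, dHD, and row 5 free of w. Estimable: dHD - dSD, which is b3.

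More children would not change the rank.

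**4. Illustrative size.** The smallest observed change that reaches p<0.05 is 2^(1.96 x SD/sqrt(80)), with SD in log2 units:

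- SD 0.6: 1.10-fold
- SD 0.8: 1.13-fold
- SD 1.2: 1.20-fold

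With SDs of 0.7, 1.0 and 1.4 on the natural-log scale (about 1.0, 1.4 and 2.0 log2), the threshold is 1.17-, 1.25- and 1.36-fold. These are observed changes. A true drift of exactly that size would be significant only about half the time.

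Suppose dose 2 adds nothing and the natural-log SD is 1.0. The standard error is 1.0/sqrt(80) = 0.112. A time ratio of 0.8 gives ln(0.8)/0.112 = -0.223/0.112 = -2.00, so row 3 or 4 is significant with probability 51%. The same holds at 1.25. At 0.9 and 1.1 it is 16% and 14%. At 0.8 or 1.25 it is 81% for SD 0.7 and 30% for SD 1.4.

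**5. Simulation check.** The 5.1 model was simplified (no covariates or site effect), with 80 per arm, no dose-2 effect and 60 data sets per setting. Assumed on the natural-log scale: between-child SD 1.2, residual SD 0.7, b1 = 0.4.

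| Time ratio | Row 3 | Row 4 | exp(b3) | Row 5 (0.67 without drift) |
|---|---|---|---|---|
| 0.8 | 0.79 | 0.80 | 1.01 | 0.54 |
| 1.25 | 1.22 | 1.23 | 1.01 | 0.82 |

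Rows 3-5 follow the time ratio; b3 does not.

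**The case against.** Titres after dose 1 and after dose 2 are routinely reported, and Table 3 is more candid than the objectives: it prints the visit numbers and labels rows 3 and 4 as within-arm. The SAP nowhere speaks of the effect of a second dose. That stands. What remains is that SAP 1.2.1 words these as group comparisons, Table 3 tests them by dose number, and no caveat is given.

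Both samples fall 28-42 days after the latest dose. If the question is titre at a fixed interval after the last dose, waning of dose 1 after Visit 2 is not a bias. It is a bias only against a one-dose child measured at Visit 3. That also stands. Infection, immunoglobulin and immune recovery remain under either question, and the SAP does not say which question it means.

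The evidence for drift is thin. Slow lymphocyte recovery does not show that HAI titres rise within weeks without vaccination. IVIG/SCIG less than 27 days before vaccination is an exclusion, and eligibility is rechecked at Visit 2. This limits one source before dose 2, but it does not protect the Visit 3 sample.

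Dose number is background in the protocol and not among its listed objectives. However, SAP 1.2.1 makes it secondary, and protocol 17b plans estimates by dose number. Children who miss dose 2 do not fill the gap: they are self-selected, and the Full Analysis Set keeps them while Table 3 labels Visit 3 as two doses.

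**Conclusion.** The point holds in a limited form. Rows 3 and 4 estimate the difference between titres 28-42 days after dose 1 and 28-42 days after dose 2 in the same children. They do not identify the effect of adding a second dose. Row 5 does compare randomised arms, but at different visits, so it mixes formulation with the same time effect. This follows from the design and needs no numerical assumption. The size and direction of any bias cannot be derived from the documents; the figures above rest on assumed SDs and time ratios.

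A reader might infer three stronger things that the documents do not support:

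- That the SAP asserts a causal effect of dose 2. It does not; that reading comes from the group wording and the null hypotheses.
- That the trial says nothing about dose 2. The before/after change on this schedule is estimable, and b3 is a randomised comparison of change.
- That this undermines the main result. Same-visit comparisons between arms, including the primary objective and row 2, are not affected by this point. The parameter that row 1 assigns to the primary comparison is a separate matter, relevant here only because the fix uses b3.

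**What to change.** In SAP 1.2.1 and Table 3:

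- Reword rows 3 and 4 as the change from Visit 2 (after dose 1) to Visit 3 (after dose 2) within arm, and row 5 as a cross-arm, cross-visit description.
- Report all three as estimates with confidence intervals, not as tests of dose number.
- State that they do not separate dose 2 from elapsed time and events between the visits. Carry the statement into the seroprotection and seroconversion analyses.
- Add exp(beta3), the HD/SD ratio of the Visit 2-to-3 changes, as the randomised between-arm contrast for this question. Note that reading it as a difference in dose-2 effect assumes similar time trends in both arms.
- Reconcile this with Table 3 row 1, which now assigns exp(beta3) to the Visit 3 between-group comparison that the 5.1 model gives as exp(beta1+beta3). Otherwise one parameter would carry two meanings.

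The cost is SAP wording, with no new data. The trial gives up a formal one-versus-two-dose test that its design cannot support.
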